9.2.1.1 Dose proportionality analysis - SAD

Dose-proportionality (an increase in dose corresponds to a proportional increase in PK outcome) after a single dose, will be assessed using the power model, i.e., linear regression modelling of $AUC_{0-\infty}$ and C_{\max} respectively on log-scale according to the formula:

$$\ln(PK) = \beta_0 + \beta_1 \times \ln(dose)$$

Let h be the highest dose and l be the lowest dose. Then the predicted PK geometric mean (back-transformed to normal scale) of the high dose is $e^{\beta_0} h^{\beta_1}$, and that of the low dose is $e^{\beta_0} l^{\beta_1}$. Let r be the maximal dose ratio, i.e., h/l . Dose proportionality corresponds to:

$$e^{\beta_0} h^{\beta_1} / e^{\beta_0} l^{\beta_1} = h/l \rightarrow (h/l)^{\beta_1-1} = r^{\beta_1-1} = 1$$

Let $\Theta_L=0.8$ and $\Theta_H=1.25$ be the lower and upper acceptance limits respectively, (0.8 and 1.25 being the industry standard limits). Dose-proportionality occurs when

$$\Theta_L < r^{\beta_1-1} < \Theta_H,$$

which on natural log scale equates to

$$\ln(\Theta_L) < (\beta_1 - 1)\ln(r) < \ln(\Theta_H) \rightarrow 1 + \frac{\ln(\Theta_L)}{\ln(r)} < \beta_1 < 1 + \frac{\ln(\Theta_H)}{\ln(r)}$$

Specifically, dose-proportionality is declared when the 90% CI for β_1 from the linear regression model on log scale lies entirely within the acceptance region:

$$\left[1 + \frac{\ln(0.8)}{\ln(r)}, 1 + \frac{\ln(1.25)}{\ln(r)} \right]$$

Dose proportionality analysis will include all the SAD fasted cohorts (including data from the fasting part of the sub-study).

9.2.1.2 Dose proportionality analysis - MAD

Dose proportionality after last dose for the MAD part of the study will be based on $AUC_{0-\tau}$ and C_{\max} . The dose proportionality analyses will be performed if data from three or more dose levels are available.

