- SAD part: Area under the plasma concentration-time curve $AUC_{0-\infty}$, AUC_t , AUC_{0-24h} , maximum concentration (C_{max}), time to maximum concentration (T_{max}), terminal elimination rate constant (λ_{dz}), terminal half-life ($T_{1/2}$), total apparent clearance of drug from plasma (CL/F), volume of distribution (V_z/F), amount excreted in urine (A_e), fraction of the dose excreted in urine (F_e) (for IRL757), renal clearance CL_R .
- Relative bioavailability after fed and fasting conditions determined from AUC_t and $AUC_{0-\infty}$, and C_{max} .
- MAD part, Day 1: $AUC_{0-\tau}$, C_{max} , T_{max} , λ_{dz} , $T_{1/2}$, Day 10: $AUC_{0-\tau}$, C_{max} , T_{max} , λ_{dz} , $T_{1/2}$, CL/F , V_z/F , fraction of the dose excreted in urine (F_e) (for IRL757) for the last dose interval in the morning of Day 10, renal clearance CL_R .
- Dose proportionality after single dose based on $AUC_{0-\infty}$ and C_{max} .
- Dose proportionality after multiple doses based on $AUC_{0-\tau}$ and C_{max} .
- Accumulation ratio (AR) after multiple doses based on C_{max} ratio and ratio $AUC_{0-\tau}$ (Day 10) to $AUC_{0-\tau}$ for the first dose interval on Day 1.

Exploratory endpoints

- Metabolite In Safety Testing (MIST) analysis of the metabolite profile in plasma in comparison with the metabolite profile in plasma from non-clinical safety studies.
- Profile of excreted metabolites in the urine.

Number of subjects planned

In the SAD part of the trial, forty (40) healthy subjects will be included (5 cohorts, 8 subjects in each cohort, randomised 3:1). Six (6) additional subjects will be included in a food interaction sub-study.

In the MAD part of the trial, up to 36 healthy subjects will be included in 2-3 cohorts with twelve (12) subjects in each cohort (up to 3 cohorts depending on the results of the SAD part of the trial, 12 subjects in each cohort, randomised 3:1).

If indicated by emerging data and recommended by the internal safety review committee (iSRC), 1 optional cohort (8 subjects) may be added to the SAD part of the trial, and 1 optional cohort (12 subjects) to the MAD part of the trial.

Diagnosis and main eligibility criteria

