Eligible subjects will be confined to the research clinic from the evening before each dosing (Day -1) until 48 hours post-dose (Day 3). The subjects should be fasting overnight (10 hours) before dose administration on Day 1. During the in-clinic period, PK blood sampling and urine sampling will be performed, from IMP administration until 48 hours post-dose and until 24 hours post-dose respectively.

A Follow-up Visit will be performed 5-10 days after administration of Investigational Medicinal Product (IMP).

The food interaction sub-study will include six (6) additional subjects. The six subjects will be administered IRL757 in fasted and fed conditions. A standardized breakfast meal will be consumed within 30 minutes prior to IMP administration, in order to study potential food interactions. After the completion of cohort 4, safety and PK data will be evaluated to determine which dose level will be used for the food interaction sub-study. For each administration, the subjects will be confined to the research clinic from the evening before dosing (Day -1) until at least 48 hours after administration (Day 3).

In the MAD part of the trial, 24 or 36 eligible and consenting subjects will be allocated to one of two (2) or three (3) cohorts; IRL757 Dose Level 1, IRL757 Dose Level 2, and IRL757 Dose Level 3 if applicable, with 12 subjects in each cohort. Within each cohort subjects will be randomly assigned to treatment with placebo or IRL757; three (3) subjects will be given placebo, and nine (9) subjects will be given IRL757.

The 12 subjects in a cohort will be divided into four (4) groups; a sentinel group, two (2) groups of three (3) subjects each and one (1) group of four (4) subjects. In each cohort, the “sentinel group” of two (2) subjects (one [1] active drug/ one [1] placebo) will be dosed first and closely observed for 24 hours before starting the dosing in the following group. Subsequent groups in the cohort will be dosed approximately 24 hours apart. In each group the subjects will be dosed with an interval of at least 30 minutes between subjects. It is foreseen that subjects will be treated with two (2) daily oral doses of IRL757 or placebo administered at the same time during ten (10) consecutive days (the dosing interval is subject to change and will be confirmed depending on the results from the SAD part of the trial).

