There will be an interval of at least one (1) week between last administration in a cohort and initiation of next cohort to allow time for PK and safety data to be analysed, evaluated and reviewed by the iSRC. The iSRC will have the choice to recommend to escalate the dose as planned, reduce or increase the dose escalation step, repeat the dose, reduce the dose or terminate the trial.

The decision on dose levels will be done following the SAD part of the trial and a cautious selection of dose will be done if dosing is expected to approach the exposure limit.

Screening (Visit 1) will take place between Day -28 and Day -1.

Eligible subjects will be confined to the research clinic from the evening before first dosing (Day -1) until Day 11 and will come back to the clinic on Day 12 for extended PK and safety samples (including 48 hours post the last morning dose). The subjects should be fasting overnight (10 hours) before dose administration on Day 1 and Day 10. A Follow-up Visit will be performed 5-10 days after last administration of IMP.

An additional third cohort (IRL757 Dose Level 3), with twelve (12) additional subjects may be implemented following the review of data of the SAD part of the trial. The cohorts are described in Table 2.

Table 2 MAD dosing groups

Cohort	Dose	Groups	
Cohort 1 (n=12)	Dose Level 1	2 + 3 + 3 + 4	Sentinel group (n=2): 1 active, 1 placebo Subsequent groups (n=3+3+4): 8 active, 2 placebo
Cohort 2 (n=12)	Dose Level 2	2 + 3 + 3 + 4	
Cohort 3 (n=12)	Dose Level 3	2 + 3 + 3 + 4	

Investigational Medicinal Products (IMP), dosage and mode of administration

IRL757 half-life is expected to be 2-7 hours.

IRL757 capsules [REDACTED]

Placebo capsules: [REDACTED]

Duration of treatment

Subjects included in the SAD part will be treated with one (1) single oral dose of IRL757 or placebo (see Table 1).

Subjects included in the food interaction sub-study will be treated with two (2) oral doses of IRL757.

Subjects included in the MAD part will receive two (2) daily oral doses of IRL757 or placebo for ten (10) consecutive days. The number of daily doses in the MAD part of the trial will be confirmed following review of PK data from the SAD part of the trial.

Duration of each subject's involvement in the trial

Subjects will be screened for eligibility according to trial-specific inclusion/exclusion criteria at Visit 1 (Screening visit) within four (4) weeks prior to start of IMP administration.

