| 
 To determine the single and multiple dose PK characteristics of IRL757 and its 3 main metabolites in healthy volunteers. To evaluate the interaction with food after single oral dosing of IRL757 on its PK characteristics and its 3 main metabolites in healthy volunteers. | 
 SAD part: Area under the plasma concentration-time curve $AUC_{0-\infty}$, AUC_t, AUC_{0-24h}, maximum concentration (C_{max}), time to maximum concentration (T_{max}), terminal elimination rate constant (λ_{dz}), terminal half-life ($T_{1/2}$), total apparent clearance of drug from plasma (CL/F), volume of distribution (V_z/F), amount excreted in urine (A_e), fraction of the dose excreted in urine (F_e) (for IRL757), renal clearance CL_R. Amount excreted in urine (A_e) for the metabolites. Relative bioavailability after fed and fasting conditions determined from AUC_t and $AUC_{0-\infty}$, and C_{max}. | PK plasma and urine sampling | Descriptive statistics and dose proportionality analysis, Section 9.2.1 | SAD: Sections 10.2.3.1, 10.3.1.1 and 10.3.1.2 MAD: Sections 11.2.3.1, 11.3.1.1 and 11.3.1.2 |

| Objectives | Endpoints | Assessments | Analyses | Data display plan (DDP) |
|---|---|----------------------------------|---|-------------------------|
| | 
 • MAD part, Day 1: $AUC_{0-\tau}$, C_{max}, T_{max}, λ_{dz}, $T_{1/2}$, Day 10: $AUC_{0-\tau}$, C_{max}, T_{max}, λ_{dz}, $T_{1/2}$, CL/F, V_z/F, fraction of the dose excreted in urine (F_e) (for IRL757) for the last dose interval in the morning of Day 10, renal clearance CL_R. Amount excreted in urine (A_e) for the metabolites. • Dose proportionality after single dose based on $AUC_{0-\infty}$ and C_{max}. • Dose proportionality after multiple doses based on $AUC_{0-\tau}$ and C_{max}. • Accumulation ratio (AR) after multiple doses based on C_{max} ratio and ratio $AUC_{0-\tau}$ (Day 10) to $AUC_{0-\tau}$ for the first dose interval on Day 1. | | | |
| Exploratory objectives | Exploratory endpoints | | | |

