4.3 Randomisation and number of subjects

In both the SAD and MAD part of the trial, subjects in each cohort will be randomised to treatment with either IRL757 or placebo (3:1). Sentinel-dosing will be applied.

Forty (40) healthy subjects will be included in the SAD part of the trial.

Six (6) additional healthy subjects will be included in the food interaction sub-study.

The MAD part of the trial will include 24 or 36 healthy subjects, depending on the number of dose levels assessed, and defined following review of the data of the SAD part of the trial (two (2) or three (3) dose levels).

In the MAD part, up to twelve (12) additional subjects may also be included if recommended by the internal safety review committee.

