5.6 Significance level

All statistical hypotheses in this trial will be answered using two-sided 90% confidence intervals.

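### With two MAD dose levels, one of the two planned scenarios, SAP 9.2.1.2 reports no between-dose ratio or confidence interval for the multiple-dose proportionality endpoint

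*SAP*

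**What the plan says.** The secondary endpoints in the protocol synopsis and in SAP Table 1 (Section 4.2) both include an entry beginning "Dose proportionality after multiple doses based on", followed by AUC0-tau and Cmax. Neither entry sets a minimum number of dose levels. SAP 5.1 adds that the trial aims to test proportionality of AUC and Cmax to dose, and refers to 9.2.1.1 and 9.2.1.2 for details.

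The number of MAD levels is open by design. The protocol synopsis says "24 or 36 eligible and consenting subjects will be allocated to one of two (2) or three (3) cohorts", and SAP 4.3 says "The MAD part of the trial will include 24 or 36 healthy subjects, depending on the number of dose levels assessed". According to the synopsis, the third cohort "may be implemented following the review of data of the SAD part of the trial". It also allows "1 optional cohort (12 subjects) to the MAD part of the trial" if emerging data call for it. In each cohort, "three (3) subjects will be given placebo, and nine (9) subjects will be given IRL757".

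SAP 9.2.1.2 then states: "The dose proportionality analyses will be performed if data from three or more dose levels are available". It gives no reason for the threshold and no alternative for two levels. The table of changes from the protocol in SAP Section 6 does not mention it.

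**The concern.** A secondary endpoint is listed without a condition, and one of the two declared design scenarios leads to no analysis of it. In that scenario the dose-proportionality figures planned in SAP 11.3.1.2 would not be produced, and the MAD table shells in SAP 11.2.3.1 contain no comparison between doses. Each dose level would be summarised separately, and readers would have to make the comparison themselves.

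The SAP's criterion does not need three levels. It judges the departure from proportionality between the highest and lowest dose, and two levels identify that quantity. If the approach is left until the two-level case arises, any ratio added then would be post hoc.

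**Working it through.** The documents state no power or precision for this analysis, so there is no figure of theirs to reproduce. The planned counts agree: 2 × 12 = 24, 3 × 12 = 36, and 3:1 randomisation of 12 gives 9 active.

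**Inputs**
- Nine active subjects per level (protocol synopsis).
- 90% two-sided intervals (SAP 5.6: "All statistical hypotheses in this trial will be answered using two-sided 90% confidence intervals").
- Power model ln(PK) = β0 + β1 ln(dose), with r the highest dose divided by the lowest, and limits 0.80 to 1.25 for r^(β1−1) (SAP 9.2.1.1). SAP 11.3.1.2 applies this acceptance region to the MAD part.
- σ, the between-subject SD of ln(PK), is not given, so results are in units of σ first and then for assumed CVs.

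**Two levels.** The fitted slope is the difference in mean ln(PK) divided by ln(r). Hence r^(β1−1) = (GM_high/GM_low)/r = (GM_high/dose_high)/(GM_low/dose_low), where GM is the geometric mean. This is the ratio of dose-normalised geometric means. On the log scale its 90% half-width is t(0.95, 16) × σ × √(1/9 + 1/9) = 1.746 × 0.4714σ = 0.823σ.

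**Three levels, middle dose at the log-midpoint.** With log-dose scaled to 0, 0.5 and 1, the sum of squares about the mean is 9 × (0.25 + 0 + 0.25) = 4.5. The half-width is t(0.95, 25) × σ/√4.5 = 1.708 × 0.4714σ = 0.805σ.

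The ratio is 0.823/0.805 = 1.022. The standard error is the same in both designs, and only the degrees of freedom differ. The result does not depend on r.

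**Middle dose off-centre**
- At 80% of the log range the sum of squares is 9 × (0.36 + 0.04 + 0.16) = 5.04 and the half-width is 0.761σ. Two levels are 8.2% wider.
- At 25% the sum of squares is 4.875 and the half-width is 0.774σ. Two levels are 6.4% wider.

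**Fewer evaluable subjects.** With 8 or 7 per level and a log-midpoint middle dose, two levels are 2.6% or 3.1% wider.

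**Assumed CVs**, with σ = √ln(1 + CV²). The CI factor is exp(half-width). The chance of meeting 0.80–1.25 is simulated at β1 = 1 with 200,000 draws.

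| CV (assumed) | σ | CI factor, 2 levels | CI factor, 3 levels | Chance, 2 levels | Chance, 3 levels |
|---|---|---|---|---|---|
| 15% | 0.149 | 1.131 | 1.128 | 0.84 | 0.85 |
| 20% | 0.198 | 1.177 | 1.173 | 0.48 | 0.50 |
| 25% | 0.246 | 1.225 | 1.219 | 0.19 | 0.20 |
| 30% | 0.294 | 1.273 | 1.267 | 0.06 | 0.05 |

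**Third dose that widens the range**, for example r = 2 with two levels and r = 4 with three. The half-width for the raw slope is 1.187σ against 0.581σ, so 2.04 times wider with two levels. The acceptance region for the slope narrows as well, from 0.678–1.322 to 0.839–1.161. On the r^(β1−1) scale the comparison remains 0.823σ against 0.805σ.

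**The case against.** A reader might infer that the endpoint is abandoned and the question left unanswerable with two levels. The documents do not support that. The synopsis describes the trial's statistics as descriptive, and SAP 9.2.1 keeps geometric means and geometric CVs of AUC0-tau and Cmax by dose group. SAP 9.2.1 also defines steady-state CL/F as dose divided by AUC0-tau, and Table PP 2 reports it. The low/high ratio of geometric mean CL/F is therefore already the AUC ratio sought here. For Cmax one divides the tabulated geometric means by dose, and the intervals could be rebuilt by hand from n and geometric CV. What is missing is the printed ratio and interval, not the data.

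The threshold also has some merit. SAP Table 1 points to Section 9.2.1, so within the SAP the three-level rule is a pre-specified condition and not a contradiction. With two levels the model is saturated and log-linearity cannot be checked, so declining a formal conclusion is defensible. That stands as a reason to withhold a verdict. It is not a reason to withhold the estimate, and the SAP does not offer it as its reason.

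Finally, the gap is conditional. A third cohort and a further optional cohort are both provided for, and the MAD table shells carry three active columns. Even so, two levels is an explicitly planned outcome. A third cohort that repeated a dose, which the synopsis allows the safety review committee to recommend, would also leave two levels.

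**Conclusion.** The gap is real but limited. In the planned two-level scenario, SAP 9.2.1.2 leaves a listed secondary endpoint without a between-dose ratio or confidence interval for AUC0-tau or Cmax, while the by-dose summaries and CL/F remain.

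The precision lost by having two levels is small on the SAP's own scale: about 2% with a log-midpoint middle dose, and up to about 8% with the middle dose between 25% and 80% of the log range. This assumes nine evaluable active subjects per level and a common σ.

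Two stronger readings should be avoided:
- Two levels are not as good as three for every purpose. The raw slope is estimated much less precisely if the third dose widens the range, and linearity between doses is untestable with two.
- The SAP's pass/fail rule need not be carried over to two levels. Over the assumed CVs of 15% to 30%, a truly proportional drug would meet the limits with probability falling from about 84% to about 6%. Three levels do no better in any material way, so the low figures argue for reporting an estimate, not for leaving the analysis out.

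**What to change.** Add to SAP 9.2.1.2 that, with two dose levels, the high/low ratio of dose-normalised geometric means for AUC0-tau and Cmax after the last dose will be reported with its 90% CI. Present it as an estimate, without a formal declaration of proportionality, and state that log-linearity cannot be checked with two levels. Keep the power model and decision rule for three or more levels. Record the three-level condition in SAP Section 6, with its reason, because the protocol synopsis lists the endpoint without it.

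The cost is a short addition to the text and one small table, with no extra subjects or samples. The two-level result will still lack a lack-of-fit check, which the added wording discloses.

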9.3 Analysis of exploratory endpoints

The analyses and results pertaining to the exploratory endpoints, MIST analysis and urine metabolite profile, will be detailed in a separate report, and hence are not covered in this SAP.

9.4 Description of trial population

9.4.1 Disposition

A subject disposition will be presented by part showing the number of screened subjects; the number of withdrawn subjects prior to dose, including the reason for withdrawal; the number of included subjects in each cohort; the number of withdrawn subjects, including the reason for withdrawal; the number of completed subjects; the number of subjects included in the analysis sets, and the number of subjects at each visit.

9.4.2 Demographics and baseline characteristics

Descriptive statistics of demographics and other baseline characteristics will be presented by part, treatment and dose group.

9.4.3 *Medical history and concomitant medication*

Medical/surgical history and prior/concomitant medications will be presented by descriptive statistics by part, treatment and dose group.

Medications are classified as prior if the stop date and time was before or on the day of the dose administration (pre-dose) and as concomitant if ongoing on the day of the dose administration, stopped after the dose administration or started after the dose administration. To distinguish between prior and concomitant medications on the dosing day, the start time of any newly introduced medication or the stop time of any previously ongoing medication will be considered.

Medical/surgical history will be summarised by SOC and PT using the MedDRA vocabulary.

Prior and concomitant medications will be summarised by ATC classification and active ingredients using the World Health Organisation (WHO) WHODrug Global drug reference dictionary.

9.4.4 *Treatment compliance*

The subjects treated in each part and treatment dose group and their individual doses will be listed.

9.5 *Interim analysis*

No formal interim analysis will be performed.

10 DATA DISPLAY PLAN - SAD

Tables and figures will only be generated if sufficient data, with sufficient variability exist to justify specific output being produced. Unscheduled/extra visits will generally not be presented in tables and summary figures but will be included in listings.

10.3 Trial figures - SAD

10.3.1 Secondary endpoints

10.3.1.1 Pharmacokinetic analysis

Figure PC 1 Geometric mean plasma concentrations of IRL757 over time 0-48h (lin-log) - SAD (Pharmacokinetic analysis set)

The figure will also include the mean curve for the fasted part of the sub-study.

Example figure. Note that the numbers do not reflect real data. This template figure will be adjusted as needed depending on the collected data.

Data based on [population]. LLOQ is xx (unit). See listing 16.2.5-1 for a per subject LLOQ summary. lin: Linear. SAS program: [PROGRAM NAME].sas. Dataset version: ADXX YYYY-MM-DDTHH:MM:SS. Run by: [USERNAME] YYYY-MM-DDTHH:MM:SS. EDC data extracted: YYYY-MM-DDTHH:MM:SS.

Figure PC 2 Geometric mean plasma concentrations of IRL757 over time 0-48h (lin-lin) - SAD (Pharmacokinetic analysis set)

Same layout as Figure PC 1. The figure will also include the mean curve for the fasted part of the sub-study.

Figure PC 3 Geometric mean plasma concentrations of IRL757 over time 0-48h (lin-log) - SAD sub-study: food interaction (Pharmacokinetic analysis set)

Same layout as Figure PC 1

Figure PC 4 Geometric mean plasma concentrations of IRL757 over time 0-48h (lin-lin) - SAD sub-study: food interaction (Pharmacokinetic analysis set)

Same layout as Figure PC 1

Figure PC 5 Geometric mean plasma concentrations of 3 main metabolites over time 0-48h (lin-log) - SAD (Pharmacokinetic analysis set)

Same layout as Figure PC 1. The figure will also include the mean curve for the fasted part of the sub-study.

Figure PC 6 Geometric mean plasma concentrations of 3 main metabolites over time 0-48h (lin-lin) - SAD (Pharmacokinetic analysis set)

Same layout as Figure PC 1. The figure will also include the mean curve for the fasted part of the sub-study.

Figure PC 7 Geometric mean plasma concentrations of 3 main metabolites over time 0-48h (lin-log) - SAD sub-study: food interaction (Pharmacokinetic analysis set)

[figure not shown]
Same layout as Figure PC 1

Figure PC 8 Geometric mean plasma concentrations of 3 main metabolites over time 0-48h (lin-lin) - SAD sub-study: food interaction (Pharmacokinetic analysis set)

Same layout as Figure PC 1

Figure PC 9 Individual plasma concentrations of IRL757 over time 0-48h by treatment (lin-log) - SAD (Full analysis set)

Individual values under LLOQ will be excluded from the figure. The full analysis set is used for individual graphs to ensure all data are plotted. However, ensure to clarify in a footnote if a subject is not in PKAS and why.

[figure not shown]

Example figure. Note that the numbers do not reflect real data. This template figure will be adjusted as needed depending on the collected data.

Data based on [population]. Individual values under LLOQ are excluded from the figure. LLOQ is xx (unit). See listing 16.2.5-1 for a per subject LLOQ summary. SAS program: [PROGRAM NAME].sas. Dataset version: ADXX YYYY-MM-DDTHH:MM:SS. Run by: [USERNAME] YYYY-MM-DDTHH:MM:SS. EDC data extracted: YYYY-MM-DDTHH:MM:SS.

Figure PC 10 Individual plasma concentrations of IRL757 over time 0-48h by treatment (lin-lin) - SAD (Full analysis set)

Individual values under LLOQ will be excluded from the figure. The full analysis set is used for individual graphs to ensure all data are plotted. However, ensure to clarify in a footnote if a subject is not in PKAS and why.

Example figure. Note that the numbers do not reflect real data. This template figure will be adjusted as needed depending on the collected data.

Data based on [population]. Individual values under LLOQ are excluded from the figure. LLOQ is xx (unit). See listing 16.2.5-1 for a per subject LLOQ summary. lin: Linear. SAS program: [PROGRAM NAME].sas. Dataset version: ADXX YYYY-MM-DDTHH:MM:SS. Run by: [USERNAME] YYYY-MM-DDTHH:MM:SS. EDC data extracted: YYYY-MM-DDTHH:MM:SS.

Figure PC 11 Individual plasma concentrations of IRL757 over time 0-48h by treatment (lin-log) - SAD sub-study: food interaction (Full analysis set)

[figure not shown]
Same layout as Figure PC 9

Figure PC 12 Individual plasma concentrations of IRL757 over time 0-48h by treatment (lin-lin) - SAD sub-study: food interaction (Full analysis set)

Same layout as Figure PC 10

Figure PC 13 Individual plasma concentrations of IRL757 over time 0-48h by subject (lin-log) - SAD sub-study: food interaction (Full analysis set)

[figure not shown]
Individual values under LLOQ will be excluded from the figure. The full analysis set is used for individual graphs to ensure all data are plotted. However, ensure to clarify in a footnote if a subject is not in PKAS and why.

Example figure. Note that the numbers do not reflect real data. This template figure will be adjusted as needed depending on the collected data.

[figure not shown]
Data based on [population]. Individual values under LLOQ are excluded from the figure. LLOQ is xx (unit). See listing 16.2.5-1 for a per subject LLOQ summary. lin: Linear. SAS program: [PROGRAM NAME].sas. Dataset version: ADXX YYYY-MM-DDTHH:MM:SS. Run by: [USERNAME] YYYY-MM-DDTHH:MM:SS. EDC data extracted: YYYY-MM-DDTHH:MM:SS.

Figure PC 14 Individual plasma concentrations of IRL757 over time 0-48h by subject (lin-lin) - SAD sub-study: food interaction (Full analysis set)

Example figure. Note that the numbers do not reflect real data. This template figure will be adjusted as needed depending on the collected data.

Data based on [population]. Individual values under LLOQ are excluded from the figure. LLOQ is xx (unit). See listing 16.2.5-1 for a per subject LLOQ summary. SAS program: [PROGRAM NAME].sas. Dataset version: ADXX YYYY-MM-DDTHH:MM:SS. Run by: [USERNAME] YYYY-MM-DDTHH:MM:SS. EDC data extracted: YYYY-MM-DDTHH:MM:SS.

Figure PP 1 Mean amount excreted in urine (Ae) over time for IRL757 - SAD (Pharmacokinetic analysis set)

Example figure. Note that the numbers do not reflect real data. This template figure will be adjusted as needed depending on the collected data.

[figure not shown]
Data based on [population]. Individual values under LLOQ are excluded from the figure. LLOQ is xx (unit). See listing 16.2.5-1 for a per subject LLOQ summary. lin: Linear. SAS program: [PROGRAM NAME].sas. Dataset version: ADXX YYYY-MM-DDTHH:MM:SS. Run by: [USERNAME] YYYY-MM-DDTHH:MM:SS. EDC data extracted: YYYY-MM-DDTHH:MM:SS.

Figure PP 2 Mean amount excreted in urine (Ae) over time for 3 main metabolites -SAD (Pharmacokinetic analysis set)

Same layout as Figure PP 1

Figure PP 3 Mean fraction excreted (Fe) over time for IRL757 - SAD (Pharmacokinetic analysis set)

Same layout as Figure PP 1

*10.3.1.2 Dose proportionality analysis***Figure PP 4 Dose proportionality for Cmax - SAD (Pharmacokinetic analysis set)**

Example figure. Note that the numbers do not reflect real data.

Include a footnote with the regression equation. Include a footnote with the 90% CI for the slope parameter/coefficient in the model, the calculated acceptance region described in Section 9.2.1.1 and the conclusion of dose-proportionality/non-dose-proportionality. It will also be specified in the footnote which data are used.

Figure PP 5 Dose proportionality for AUC_{0-inf} - SAD (Pharmacokinetic analysis set)

Same layout as Figure PP 4

